9.4.5 BASELINE DESCRIPTIVE STATISTICS

The following will be reported as baseline descriptive statistics in the two groups:

- Age
- Gender
- Race/ethnicity
- Location of cardiac arrest
- Cardiac arrest witnessed
- Bystander CPR performed
- Time from 911 call to EMS arrival at patient, minutes
- Time from 911 call to arrival at CCL/MED, minutes
- Time from 911 call to ECLS application, minutes
- Time from CCL entry to ECLS, minutes
- CCL entry to balloon time, minutes
- Incidence of Return of Spontaneous Circulation (ROSC)

- Resuscitation therapies administered
 - Drugs and doses administered
 - Number of shocks
 - Type and success of advanced airway
 - Therapeutic hypothermia

9.4.6 PLANNED INTERIM ANALYSES

An independent DSMB will be appointed in order to ensure the safety of the subjects by monitoring adverse outcomes throughout the trial and by reviewing outcome data for both efficacy and possible harm. At least one bioethicist will be included in the DSMB membership. In addition, the Board will review the results of interim analyses. The DSMB must review and approve the protocol before the study can commence. The DSMB will evaluate the rate of adverse events between the treatment and control arms at 6-month intervals. As noted above, the DSMB will be notified whenever the randomization allocation ratio is changed. The DSMB will be required to conduct a formal vote on a recommendation to stop the study if the posterior probability that one group is superior to the other exceeds 0.986. The DSMB will also monitor secondary study outcomes success rates between the treatment and control groups, and rates of adverse events.

9.4.7 SUB-GROUP ANALYSES

The primary study endpoint will be compared between: 1) males versus females, 2) study subjects < 55 versus ≥55 years old, 3) presence versus absence of coronary artery disease (>70% stenosis), and 4) 911 call to ECMO initiation <50 versus ≥50 minutes. It should be noted, however, that *a priori*, the power to detect significant treatment effects in these subgroups, which are substantially smaller than the trial's entire cohort, will be low. These are exploratory. The sample sizes of these defined subgroups are such that the power to test hypotheses in these subgroups is substantially smaller than that for the main hypothesis.

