4.2 SUBGROUP ANALYSES

The primary study endpoint will be compared between: 1) males versus females, 2) study subjects < 55 versus ≥ 55 years old, 3) presence versus absence of coronary artery disease (>70% stenosis), and 4) 911 call to ECMO initiation < 50 versus ≥ 50 minutes. It should be noted, however, that *a priori*, the power to detect significant treatment effects in these subgroups, which are substantially smaller than the trial's entire cohort, will be low.

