Standard ACLS Resuscitation. If the patient is randomized to this protocol, research personnel will notify the ED MD about the randomization. Patients who have not achieved ROSC continue on ACLS resuscitation after arrival in the ED. Patients receive continued ACLS treatment in the ED for at least 15 minutes following ED arrival or at least 60 minutes from 911 call. If ROSC is achieved in the ED, the CCL team is mobilized and the patient transferred to the CCL per standard University of Minnesota clinical practice. If the patient has ROSC in the ED, but continues to re-arrest, the CCL team will not be mobilized until the patient demonstrates ROSC (as determined by the treating clinician, consistent with current clinical practice). If the ED MDs deem the ACLS effort futile at any point after 15 minutes of CPR from ED arrival or 60 minutes after the 911 if known, they can declare death.

Patients presenting or achieving ROSC in both group arms.

All patients with ROSC and pulses after VF/pVT OHCA gain access to the CCL per standard of care at the University of Minnesota. As such, those patients, in both groups will go to the CCL **regardless of arm allocation.**

VA ECMO or other circulatory support device initiation in those patients is based on the interventional cardiologist's clinical judgment. In general, evidence of the following are common indications for VA ECMO initiation in all CCL patients:

- i) Profound cardiogenic shock with SBP < 90 mmHg or MAP < 60mmHg despite inotropic support and an intra-aortic balloon pump,
- ii) Persistent hypoxia with arterial oxygen saturation < 90% despite maximum ventilatory support,

- iii) Florid pulmonary edema despite IV diuretics,
- iv) Recurrent episodes of VF or VT in the CCL.

Post-resuscitation Critical Care Recommended Pathway

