6.3 MEASURES TO MINIMIZE BIAS: RANDOMIZATION AND BLINDING

Patients eligible for this study will be VT/VF OHCA patients refractory to standard treatment as defined by the ARREST Trial inclusion and exclusion criteria. Initially patients will be randomly allocated in a 1:1 ratio immediately following hospital arrival. As noted in the Statistical Considerations section, this trial has a Bayesian Adaptive Design, which means that the treatment allocation ratio may be changed later to reduce the probability of assignment to an inferior treatment arm. See Section 9 below. The study has been designed to minimize treatment bias as far as possible. EMS providers will be blinded to the study. University of Minnesota Refractory VF/VT Protocol patients are placed on LUCAS and transferred to the University of Minnesota with ongoing mechanical CPR per standard of care. All out-of-hospital care, including CPR, ACLS, and resuscitation efforts, will be implemented using ACLS guidelines and automated CPR (LUCAS™2) and treatment will be unchanged. Patients will be randomized and entered in the study by research personnel only after hospital arrival and assessment of ARREST Trial inclusion and exclusion criteria. Emergency department personnel will be aware of group assignment. However, ED treatment of all patients follows protocol and standard of care. CCL personnel also will be aware of group assignment, but treatment is similarly protocolized. Post-CCL care in the CICU will be blinded to group assignment. Patients in both groups could have received identical treatment. Patients from both groups will be treated with the same established CICU post arrest protocol by the same critical care team. The PIs will not be involved in any end-of-life decision making. The **Figure** below shows the phases of care in which providers are blinded to group allocation (in light blue).

Thus, we expect patients in both groups to similarly reflect the gender, ethnic diversity, severity or duration of cardiac arrest, and receive the same therapy except early ECMO facilitated resuscitation versus standard ACLS resuscitation.

[figure not shown]

Figure: Patient flow chart showing blinding.

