9.3 POPULATIONS FOR ANALYSES

The primary population for analysis is the set of patients who are randomized immediately following hospital arrival and are not excluded afterward by conditions that cannot be determined emergently. The patients that are found to meet prespecified exclusion criteria for the ARREST trial post randomization will be excluded. These are the only patients excluded from the ITT population.

It may happen in rare cases that a patient randomized to **early ECMO facilitated resuscitation** does not receive ECMO, or conversely that a patient randomized to **standard ACLS resuscitation** does receive ECMO because they became clinically unstable after they entered the CCL with ROSC. These cases, if they are found to meet eligibility and exclusion criteria, will be analyzed according to the ITT principle: 1) those randomized to receive **early ECMO facilitated resuscitation** will be classified in the early ECMO

facilitated resuscitation group irrespective of whether or not they received ECMO, and 2) those randomized to receive **standard ACLS resuscitation** will be classified in the standard ACLS resuscitation group irrespective of whether or not they received ECMO.

The secondary 'as-treated' population will be comprised of two groups of patients: (1) those who receive ECMO, regardless of treatment assignment, and (2) those who do not receive ECMO (again regardless of treatment assignment).

As specified elsewhere in this Protocol, there are pre-specified subpopulations of interest. These are defined by: 1) gender, 2) age group (< 55 years old versus \geq 55 years old), 3) presence versus absence of coronary artery disease (> 70% stenosis), and 4) 911 call to CCL arrival (< 50 minutes vs. \geq 50 minutes). These will be treated as strata in Mantel-Haenszel analyses and in multivariable logistic analyses of the data. Such analyses will include terms for interaction of the randomized treatment group assignment with the stratifying factors.

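### Angiographic CAD and time to ECMO are pre-specified subgroup factors but are observed only through post-randomisation care that differs by arm; the time factor also has two definitions

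*Combined protocol and SAP*

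**What the plan says.** **Factors.** Sections 4.2 and 9.4.7 name four subgroup factors: sex, age, CAD by stenosis, and a time split at 50 minutes. In 4.2 the time is "4) 911 call to ECMO initiation", and 9.4.7 agrees, giving its third and fourth factors as "presence versus absence of coronary artery disease (>70% stenosis), and 4) 911 call to ECMO initiation". In 9.3 it is "4) 911 call to CCL arrival", also split at 50 minutes.

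**Use.** Section 9.3 says of all four: "These will be treated as strata in Mantel-Haenszel analyses and in multivariable logistic analyses of the data". It adds: "Such analyses will include terms for interaction of the randomized treatment group assignment with the stratifying factors". It gives no rule for a patient whose factor has no value.

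**Timing and pathways.**
- Section 6.3: "Initially patients will be randomly allocated in a 1:1 ratio immediately following hospital arrival".
- Early-ECMO arm (6.1.1): patients go to the CCL whatever their ROSC status. Those who meet more than one discontinuation criterion on arrival there are declared dead.
- Standard arm (6.1.1): "If ROSC is achieved in the ED, the CCL team is mobilized and the patient transferred to the CCL". The Synopsis and Appendix A also make CCL access conditional on ROSC, and 2.3.2 says this arm does not offer ECMO to patients who are not resuscitated. Section 3 makes angiography after ROSC, in either arm, subject to clinical indication.
- Section 4.1 expects patients in either arm who never need ECMO.

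**Caveats in the plan.** Section 9.4.7 calls the subgroup analyses exploratory and low in power. Section 9.4.5 lists a time from 911 call to arrival at CCL/MED; MED is not in the abbreviation list.

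**The concern.** A subgroup factor supports a randomised comparison within its levels only if its value, and whether it is observed, cannot depend on the assigned arm. CAD itself precedes randomisation, but the documents name no source for it other than angiography, and access to angiography depends on arm. Time to ECMO arises after randomisation. So does time to CCL arrival, unless 9.3 means an arrival time at the hospital.

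A patient without a value cannot enter a stratum or a complete-case logistic model. In the standard arm those patients are the ones without ROSC, who are expected to die. Leaving them out raises control survival among those who remain, with no matching selection in the ECMO arm.

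CAD is the protocol's stated mechanism (2.1, 2.2), and the results are meant to inform a multicentre trial (2.1, 9.4.1). A CAD-stratified result that contradicts the overall result could mislead that step. The two definitions of factor 4 also leave the analyst a choice that should be closed before data are seen.

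**Working it through.** **1. Who can be classified, if 9.3 is followed with no added rule**

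| | Early-ECMO arm | Standard arm |
|---|---|---|
| CAD status | most patients; possibly not those declared dead on CCL arrival | only with ROSC and angiography |
| 911 to CCL | patients who reach the CCL | only with ROSC |
| 911 to ECMO | patients who receive ECMO | only with ROSC and ECMO |

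**2. The plan's own figures.** Simulating the design in 9.1 (10,000 trials per scenario) gives rejection rates of 0.901 under 37% versus 12% (stated 0.905) and 0.049 under the null (stated 0.048). Mean arm sizes under the alternative are 53.4 and 29.6 (stated 52.5 and 29.2). The illustration uses 52 ECMO and 29 standard patients. The plan gives no figure for the subgroup analyses.

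**3. Inputs**
- Survival 0.37 and 0.12 (9.1), so the true difference is +25 points.
- s, survival given ROSC in the standard arm: not stated, so assumed from 0.20 to 0.667. Two values come from 2.3.2: 22/33 = 66.7%, an extreme because those ROSC patients were supported with VA ECMO, and 222/411 = 54%, from patients whom 2.3.2 describes as a healthier group.
- g, share of ECMO patients with angiography: not stated, so assumed from 0.65 to 1.
- Also assumed: unclassified patients are dropped; all standard-arm ROSC patients have angiography; every survivor is classifiable; survival does not depend on CAD; no effect modification.

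Section 2.3.1 puts ROSC in general below 10%. That is less than the 12% of controls planned to survive, so it is not used as an input.

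**4. Formulas.** Control ROSC share r = 0.12/s. Survival among classified controls = 0.12/r = s. Survival among classified ECMO patients = 0.37/g. Expected CAD-stratified risk difference D = 0.37/g - s.

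| s | r | Controls without CAD status | Classifiable of 29 | D, g = 1 | D, g = 0.80 |
|---|---|---|---|---|---|
| 67% | 18% | 82% | 5.2 | -30 | -20 |
| 54% | 22% | 78% | 6.4 | -17 | -8 |
| 40% | 30% | 70% | 8.7 | -3 | +6 |
| 30% | 40% | 60% | 11.6 | +7 | +16 |
| 20% | 60% | 40% | 17.4 | +17 | +26 |

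D is in points, against a true +25. With less angiography in the ECMO arm, s = 20% and g = 0.70 give 0.37/0.70 - 0.20 = +33; s = 30% and g = 0.65 give 0.37/0.65 - 0.30 = +27.

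Simulated Mantel-Haenszel estimates at 52/29 agree with these means to within rounding. At g = 1 and s = 67%, 54%, 40% and 30%, the sign is wrong in 89%, 78%, 56% and 32% of trials, against 0.4% when all randomised patients are compared. Under the adaptive design the corresponding means are -23, -10, +4 and +13 points, against +30 for all randomised patients in the same trials.

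**5. Where the direction changes**
- The mean reverses when s > 0.37/g, that is r < 0.12g/0.37: below 32.4% at g = 1 and below 25.9% at g = 0.80.
- The bias is zero when s = 0.37/g - 0.25. At g = 0.80, s = 21.25% and r = 0.12/0.2125 = 56%. At g = 0.70, s = 27.9% and r = 43%. Above that r the bias favours ECMO.

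**6. Interaction.** Under these inputs D is the same in both CAD strata, so the treatment-by-CAD contrast is centred on zero. Simulation gave values near zero throughout.

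**7. Time to ECMO.** This is missing in at least as many controls as CAD status, and also in patients of either arm who never need ECMO. No size or direction was derived.

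**The case against.** The best defence is that these analyses are labelled exploratory and low in power, and that no decision in the documents rests on them. That limits the consequence. It does not answer the point, because low power warns of an imprecise estimate, not of one centred on the wrong value.

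Second, the plan does not prescribe dropping unclassified patients. It is silent, and a missing category would retain them. The figures above are therefore conditional. A missing category would not repair the CAD strata, though: their membership is unchanged, and if every ECMO patient has angiography the extra stratum contains no ECMO patient and has no weight.

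Third, the CCL/MED item in 9.4.5 may record hospital arrival. If 9.3 means that item, its version of factor 4 is sound. CAD and time to ECMO would still have the problem.

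Fourth, 2.2 says that both groups will receive angiography. The Synopsis, 6.1.1 and Appendix A make this conditional on ROSC in the standard arm, so the sentence in 2.2 reads as loose background wording.

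Three stronger readings are tempting, and the documents do not support them:
- A reader might infer that the stratified effect is always biased against ECMO, or will reverse. Neither survival given ROSC nor ECMO-arm angiography is stated, and some values in step 4 remove the bias or turn it in favour of ECMO. Section 2.3.2 itself describes re-arrest and early failure after ROSC, which allows a low s.
- A reader might infer that the treatment-by-CAD interaction is distorted. That would need ROSC or survival to depend on CAD. The documents do not quantify this and it was not modelled.
- A reader might take 67% as a typical value. It comes from a selected group and marks an extreme.

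**Conclusion.** The point holds in limited form and should be corrected. As written, 9.3 stratifies between-arm comparisons on angiographic CAD and on a time to ECMO or CCL, and whether these are observed depends on post-randomisation care that differs by arm. If unclassified patients are left out, the within-stratum and pooled stratified effects are not valid randomised comparisons. That conclusion rests on the care pathways alone.

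The size rests on assumptions. Over survival given ROSC of 20% to 67% and ECMO-arm angiography of 80% or 100%, the mean CAD-stratified difference lies between about -30 and +26 points for a true +25; lower angiography takes it to about +33. Bias against ECMO is likely, because its absence requires a high ROSC share (56% at g = 0.80) while 2.3.1 describes ROSC as uncommon. It is not certain.

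The conflict between 9.3 and Sections 4.2 and 9.4.7 over factor 4 is plain on the text. The primary analysis and the stopping rule do not use these strata and are unaffected.

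**What to change.** Amend 4.2, 9.3 and 9.4.7 together.

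1. Use one factor 4 that is fixed before randomisation and defined in both arms: time from 911 call to hospital arrival. First confirm that the CCL/MED item in 9.4.5 records it. Set the cut-point without reference to trial outcomes, since 50 minutes was chosen for a time to ECMO or CCL. State how an unknown 911 time is handled; 6.1.1 allows for one ("60 minutes after the 911 if known").
2. Remove angiographic CAD and time to ECMO or CCL from the between-arm strata and interaction models. Report them descriptively among patients with angiography or ECMO, without a between-arm test.
3. If the factors are to share one model, make sure that the sex and age analyses keep every randomised patient in the ITT population.

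Reconciling 2.2 with the Synopsis and 6.1.1 on who receives angiography is editorial.

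**Cost.** A minor amendment with IRB approval (Statement of Compliance), one cut-point decision and one check of a data field. The trial gives up a between-arm contrast by CAD or by time to ECMO, which this design cannot validly provide. Time to hospital arrival answers a different question from time to ECMO, and the latter would remain descriptive.

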9.4.8 TABULATION OF INDIVIDUAL PARTICIPANT DATA

Patients in this trial will have complex clinical courses prior to hospital discharge. They will experience a wide variety of adverse events, many of them serious, some of them known complications of ECMO treatment. The Statistical and Data Coordinating Center will maintain detailed histories, by hospital course day, of adverse events and treatments. Tables comprised of such detailed histories will be available for examination by members of the DSMB. DSMB summary tables will classify the nature and frequency of adverse events essentially by collapsing such histories across treatment groups and other strata of interest.

All data in SDCC files, reports, or tables will be de-identified.

9.4.9 EXPLORATORY ANALYSES

In addition to the primary and secondary analyses described above, the SDCC will carry out non-pre-specified analyses in certain subgroups. This will include time of day of the event, laboratory findings, and treatments administered during the hospital stay. Such analyses may be carried out on emergent factors which were not anticipated or described at the beginning of the trial. As such, any hypothesis testing (p-values) arising from such analyses must be regarded as exploratory. They will need to be noted and reported to the DSMB and in publications emanating from the trial, but they will also need to be confirmed by future studies and will be clearly described as exploratory.

10 SUPPORTING DOCUMENTATION AND OPERATIONAL CONSIDERATIONS

10.1 REGULATORY, ETHICAL, AND STUDY OVERSIGHT CONSIDERATIONS

10.1.1 INFORMED CONSENT PROCESS

Enrollment is initiated under an exception from informed consent as the patient is unconscious and in cardiac arrest. Enrollments will not occur until after EFIC plan and protocol approval by the relevant IRB(s).

Consent forms describing in detail the study agent, study procedures, and risks are given to the participant and written documentation of informed consent is required prior to continuing study procedures. The following consent materials are submitted with this protocol: informed consent to continue participation, notification letters, and script for objection to research.

10.1.1.1 CONSENT PROCEDURES AND DOCUMENTATION

Informed consent is a process that is initiated prior to the participant or the individual's legally authorized representative agreeing to continue to participate in the study and continues throughout the individual's study participation. Extensive discussion of risks and possible benefits of continued participation will be provided to the participants and their families along with a description of what has occurred so far given initial enrollment under EFIC. Consent forms will be IRB-approved and the participant will be asked to read and review the document. The investigator will explain the research study to the participant and answer any questions that may arise. All participants will receive a verbal explanation in terms suited to their comprehension of the purposes, procedures, and potential risks of the study and of their rights as research participants. Participants will have the opportunity to carefully review the written consent form and ask questions prior to signing. The participants should have the opportunity to discuss the study with their surrogates or think about it prior to agreeing to participate. The participants may withdraw consent at any time throughout the course of the trial. A copy of the informed consent document will be given to the participants for their records. The rights and welfare of the participants will be protected by emphasizing to them that the quality of their medical care will not be adversely affected if they decline to continue to participate in this study.

10.1.2 CONFIDENTIALITY AND PRIVACY

Participant confidentiality and privacy is strictly held in trust by the participating investigators, their staff, and the sponsor(s) and their interventions. Therefore, the study protocol, documentation, data, and all other information generated will be held in strict confidence. No information concerning the study or the data will be released to any unauthorized third party without prior written approval of the sponsor.

All research activities will be conducted in as private a setting as possible.

The study monitor, other authorized representatives of the sponsor, representatives of the Institutional Review Board (IRB), regulatory agencies or pharmaceutical company supplying study product may inspect all documents and records required to be maintained by the investigator, including but not limited to, medical records (office, clinic, or hospital) and pharmacy records for the participants in this study. The clinical study site will permit access to such records.

The study participant's contact information will be securely stored at the clinical site for internal use during the study. At the end of the study, all records will continue to be kept in a secure location for as long a period as dictated by the reviewing IRB, Institutional policies, or sponsor requirements.

Study participant research data, which is for purposes of statistical analysis and scientific reporting, will be transmitted to and stored at the University of Minnesota SDCC. This will not include the participant's contact or identifying information. Rather, individual participants and their research data will be identified by a unique study identification number. The study data entry and study management systems used by clinical sites and by University of Minnesota SDCC research staff will be secured and password protected. At the end of the study, all study databases will be de-identified and archived at the University of Minnesota SDCC.

